### **Medical History**

10. History of any of the following cardiovascular conditions within 12 months of the initiation of study treatment:
  - a. Symptomatic ischemic heart disease or unstable angina pectoris
  - b. Myocardial infarction
  - c. Cardiac angioplasty or stenting
  - d. Coronary or peripheral artery bypass graft
  - e. Class III or IV heart failure per NYHA (see [Appendix D](#))
  - f. Cerebrovascular accident or transient ischemic attack
11. Inadequately controlled hypertension (defined as SBP  $\geq 150$  mm Hg and/or DBP  $\geq 90$  mm Hg) based on an average of 3 BP readings at least 2 minutes apart.  
Note: Treatment with antihypertensive medication is allowed during screening to achieve BP with SBP/DBP  $< 150/90$  mm Hg.

12. History of hypertensive crisis or hypertensive encephalopathy.
13. Significant vascular disease (eg, aortic aneurysm requiring surgical repair or recent peripheral arterial thrombosis) within 6 months prior to initiation of study treatment.
14. History of deep vein thrombosis or pulmonary embolism within 6 months of screening.
15. History of thromboembolism while on anticoagulation therapy.
16. Active bleeding disorder or other history of clinically significant (non-GI) bleeding episodes within 30 days of enrollment.
17. History of hemoptysis (> 2.5 mL/1 teaspoon of bright red blood per episode) within 6 weeks prior to the initiation of study treatment.
18. Tumor known to invade or encase a major blood vessel.
19. Major surgical procedure within 1 month prior to initiation of study treatment or expected need for a major surgical procedure during the study.
20. Core biopsy or other minor surgical procedure, excluding placement of a vascular access device, within 3 days prior to the initiation of study treatment.
21. Clinically significant nonhealing wound, wound dehiscence, or active ulceration or untreated bone fracture.
22. History of interstitial lung disease, including noninfectious pneumonitis requiring steroids.
23. Clinically significant GI abnormality, including the following:
  - Inability to take oral medication
  - Requirement for enteral or parenteral nutrition
  - Conditions that may affect drug absorption, as well as those that interfere with GI transit, including gastric bypass surgery, gastric sleeve, or gastric band
  - Endoscopically determined active gastroduodenal ulcer(s)
  - GI condition associated with increased risk of perforation (eg, direct tumor invasion of the bowel wall, inflammatory bowel disease, ulcerative colitis) or history of GI perforation
  - Current abdominal/pelvic fistulation or a history of abdominal/pelvic fistulation within the last 12 months
  - Acute or subacute intestinal obstruction
  - GI bleeding (eg, hematemesis, hematochezia, and melena) within 3 months prior to initiation of study treatment
24. Any autoimmune disease requiring systemic treatment in the past 5 years, including corticosteroids of a daily dose exceeding 10 mg of prednisone or equivalent.  
Exceptions: Hypothyroidism stable on hormone replacement or vitiligo.
25. Diagnosis of a primary immunodeficiency.

26. Active HBV or HCV defined as follows (testing must be performed to determine eligibility):

- a. Chronic HBV infection with HBV DNA (viral load) > 500 IU/mL.

Note: Participants with chronic HBV infection who are on anti-HBV therapy and have HBV DNA < 500 IU/mL may enroll. Anti-HBV therapy must be initiated prior to initiation of study treatment and must continue while on study treatment and for 12 months after the end of study treatment.

- b. Active HCV is defined as a positive HCV antibody result and quantitative HCV RNA (viral load) result greater than the lower limit of detection for the assay.

Note: Participants previously treated for HCV with undetectable HCV RNA are allowed in the study.

27. HIV infection and any of the following:

- CD4+ T-cell count < 200 cells/ $\mu$ L

- Detectable HIV RNA

OR

- On an ART regimen containing drugs that are moderate or potent CYP3A4/CYP3A5 inhibitors or inducers.

Note: Switching to an alternative ART regimen with drugs that are weak or intermediate CYP3A4/5 inhibitors or inducers is allowed but must be taken for at least 28 days before initiating study treatment.

28. Active infection, including tuberculosis, requiring systemic therapy.

Exceptions: Hepatitis B and C and HIV infections.

29. History of organ transplant (including stem cell transplantation).

30. Known hypersensitivity or severe reaction to any component of study drug or formulation components.

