## 5. STUDY POPULATION

Deviations from eligibility criteria are not allowed because they can potentially jeopardize the scientific integrity of the study, regulatory acceptability, and/or participant safety. Therefore, adherence to the criteria as specified in this Protocol is essential. Prospective approval of Protocol deviations to recruitment and enrollment criteria, also known as Protocol waivers or exemptions, are not permitted.

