**Table 12: Axitinib Toxicity Management Guidelines (Continued)**

Event/Severity (CTCAE v5 Grade)	Management Guideline
Cardiac failure	
Asymptomatic cardiomyopathy (LVEF > 20% but < 50% below baseline or below the lower limit of normal of baseline was not obtained)	
 
Interrupt axitinib until resolution to Grade 0 or 1 or baseline.
 
Resume axitinib with a dose reduction of 1 level (see Table 9).
 

Clinically manifested CHF	Discontinue axitinib.
Fistula	
Trachea-esophageal fistula Any grade	Discontinue axitinib.
Fistula other than trachea-esophageal Grade 1 or Grade 2	
 
Interrupt axitinib.
 
Either resume axitinib at a dose reduction (see Table 9) or discontinue depending on the severity and persistence of the adverse reaction.
 

Fistula other than trachea-esophageal fistula Grade 3 or Grade 4	Discontinue axitinib.
Impaired wound healing	
Any grade	
 
The safety of resumption of axitinib after resolution of wound healing has not been established.
 
Either resume axitinib at a reduced dose (see Table 9) or discontinue, depending on the severity and persistence of the adverse reaction.
 

GI perforation	
Any grade	Discontinue axitinib.
Arterial thromboembolic events	
Any grade	Discontinue axitinib.
Venous thromboembolic events	
Any grade	
 
Interrupt axitinib.
 
Either resume axitinib at the same dose level or discontinue, depending on the severity of the VTE.
 
Permanently discontinue for severe VTE.
 

Hemorrhage	
Grade 1	
 
For hemoptysis, interrupt axitinib and evaluate underlying causes.
 
Resume axitinib at the discretion of the investigator.
 
For other Grade 1 hemorrhage/bleeding events, continue axitinib at the current dose level and monitor as clinically indicated.
 

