## **9.11. Treatment of Overdose**

Overdose is not an SAE unless it meets the criteria of an SAE (see [Section 9.2](#)).

For this study, any dose of INCB099280 or axitinib greater than the dose prescribed within a 24-hour time period will be considered an overdose and recorded in the eCRFs.

In the event of an overdose, the investigator/treating physician should do the following:

- Contact the medical monitor immediately.
- Closely monitor the participant for any AE/SAE and laboratory abnormalities until study treatment can no longer be detected systemically (at least 90 days).
- Obtain a plasma sample for PK analysis within 2 days from the date of the last dose of study treatment if requested by the medical monitor (determined on a case-by-case basis).
- Document the quantity of the excess dose as well as the duration of the overdose in the eCRF.

Decisions regarding dose interruptions or modifications will be made by the investigator in consultation with the medical monitor based on the clinical evaluation of the participant.

There has been no clinical experience with overdose of INCB099280. Treatment of overdose should consist of general supportive measures.

There is no specific treatment for axitinib overdose. In a controlled clinical study with axitinib for the treatment of patients with RCC, 1 participant inadvertently received a dose of 20 mg BID for 4 days and experienced dizziness (Grade 1; [Inlyta 2021](#)). In clinical studies, participants who received up to 10 mg BID or 20 mg BID experienced adverse reactions that included hypertension, seizures associated with hypertension, and fatal hemoptysis ([Inlyta 2021](#)). In cases of suspected overdose, axitinib should be withheld and supportive care instituted.

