## APPENDIX B. INSTRUCTIONS TO PARTICIPANTS FOR HANDLING STUDY DRUG (INCB099280)

The participant must be instructed in the handling of study drug as follows:

- INCB099280 [REDACTED]-mg tablets must be [REDACTED] Store the study drug in a [REDACTED] at [REDACTED]
- INCB099280 [REDACTED]-mg tablets are to be stored at [REDACTED]
- Only remove the number of tablets needed at the time of administration.
- Do not remove doses in advance of the next scheduled administration.
- Make every effort to take doses on schedule.
- Report any missed doses/lost tablets.
- Take study drug with approximately 240 mL (approximately 8 oz) of water.
  - Participants must swallow the tablets whole without chewing before swallowing. Tablets must not be crushed, split, or dissolved.
- Report compliance with study drug daily.
- On days of PK sampling, participants should not consume a [REDACTED] meal within at least [REDACTED] hours before or after INCB099280 dose administration.
- INCB099280 should be taken on an [REDACTED] or with a [REDACTED] meal.
  - An example of a [REDACTED] meal in the United States typically contains 11 to 14 g of fat and a total caloric value of 400 to 500 kcal (eg, 8 oz of skim [1% fat] milk, 1 boiled egg, and 1 packet of flavored instant oatmeal made with water).
  - Meals that exceed [REDACTED] calories with [REDACTED]% calories from fat should be consumed at least [REDACTED] hours before or after INCB099280 administration. Site staff should discuss light meals or snacks with the participant and provide examples of food consumption that should be avoided within the  $\pm$  [REDACTED]-hour fasting window.
- Doses should be taken in the morning and evening, approximately 12 hours apart.
  - If a dose of INCB099280 is missed by more than 4 hours, that dose should be skipped, and the next scheduled dose should be taken at the usual time.
- If vomiting occurs after taking study drug, do not take another dose.
- Keep study drug in a safe place and out of sight and reach of children.
- Bring all used and unused study drug bottles/kits to the site at each visit.

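### Exclusion 17 gives its hemoptysis limit as 2.5 mL and as 1 teaspoon, as if equal; a standard teaspoon is about 5 mL, so the criterion holds two thresholds about twofold apart

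*Protocol*

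**What the plan says.** Among the medical-history exclusions in Section 5.2, criterion 17 reads: "History of hemoptysis (> 2.5 mL/1 teaspoon of bright red blood per episode) within 6 weeks prior to the initiation of study treatment". It is the only place where the protocol gives a volume for hemoptysis. The protocol does not define a teaspoon and does not say whether the metric or the household figure decides.

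The criteria are binding. Section 5 states: "Deviations from eligibility criteria are not allowed because they can potentially jeopardize the scientific integrity of the study, regulatory acceptability, and/or participant safety". The same paragraph rules out prospective waivers.

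Three other provisions bear on the same patients:
- Criterion 16 excludes an active bleeding disorder or other clinically significant bleeding, GI bleeding apart, in the 30 days before enrollment. It sets no volume.
- Criterion 43 lets the investigator exclude a patient whose history might raise the risk of taking part or of receiving study drug.
- Table 12, on Grade 1 hemorrhage during treatment, says: "For hemoptysis, interrupt axitinib and evaluate underlying causes".

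**The concern.** A numeric eligibility limit should classify a given history one way. This one gives two answers for part of its range because its two units do not agree. Patients are likely to describe coughed-up blood in household terms, so the teaspoon is the unit a site can most readily apply at interview. It is also the more permissive of the two.

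The criterion has a safety purpose. The protocol treats bleeding as a known axitinib risk: Table 12 acts on hemoptysis at Grade 1, and Section 9.11 records that participants on up to 10 mg or 20 mg BID "experienced adverse reactions that included hypertension, seizures associated with hypertension, and fatal hemoptysis".

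There is also an administrative consequence. Because deviations are not allowed, a site or monitor must be able to say whether a participant met the criterion. A participant found ineligible may be discontinued (Section 7.1.1) and, in Part 1, may be replaced (Section 5.6). For an episode inside the disputed band, criterion 17 as written does not settle that status.

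**Working it through.** **Inputs**
- Stated limits, criterion 17: more than 2.5 mL, or 1 teaspoon, per episode.
- Look-back, criterion 17: 6 weeks = 42 days before the start of treatment.
- Look-back, criterion 16: 30 days before enrollment.
- Gap from enrollment to treatment, Section 8.1.2: at most 3 days.
- Size of a teaspoon: not in the protocol. Taken as an assumption from standard unit definitions, with the range shown.

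**Step 1: try to reproduce 2.5 mL = 1 teaspoon**

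| Definition | mL per teaspoon | Ratio to 2.5 mL | 2.5 mL in teaspoons |
|---|---|---|---|
| US customary: 231 in³ × 16.387064 mL/in³ ÷ 768 | 4.93 | 1.97 | 0.51 |
| Metric | 5.0 | 2.00 | 0.50 |
| Imperial | 5.92 | 2.37 | 0.42 |

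None of these definitions gives 2.5 mL. The stated figure corresponds to about half a teaspoon.

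**Step 2: a rough cross-check**

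Appendix B says: "Take study drug with approximately 240 mL (approximately 8 oz) of water". That implies 240 ÷ 8 = 30 mL per ounce. At 6 teaspoons per ounce, 30 ÷ 6 = 5 mL per teaspoon. The 6-per-ounce step is a unit definition from outside the protocol, so this shows agreement with the table and nothing more.

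**Step 3: classify an episode of volume V within the 42 days, under criterion 17 alone**

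| V | By the mL limit | By the teaspoon limit |
|---|---|---|
| up to 2.5 mL | not excluded | not excluded |
| above 2.5 mL, up to about 5 mL | excluded | not excluded |
| above about 5 mL | excluded | excluded |

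Only the middle row is in conflict. Reading the slash as an alternative does not give the teaspoon a role: anything above about 5 mL already exceeds 2.5 mL, so the teaspoon figure would be redundant.

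**Step 4: how much of the window criterion 16 also covers**

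Thirty days before enrollment is 30 to 33 days before treatment, given a gap of 0 to 3 days. The part of the 42-day window that it does not reach is 42 − 33 = 9 days to 42 − 30 = 12 days. An episode in those earliest 9 to 12 days falls to criterion 17 and to general investigator judgment under criterion 43.

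**The case against.** The best case on the other side is that the slip has little practical effect.

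- **Other criteria catch some of these patients.** This stands. Hemoptysis is non-GI bleeding, so criterion 16 applies whenever the investigator judges the episode clinically significant. A 3 to 5 mL episode three weeks before treatment lies inside its 30-day window and could be excluded whichever unit is used for criterion 17. Criterion 43 gives further discretion and is an ordinary criterion, not a waiver. A reader might infer that nothing else in the protocol can correct the error; the documents do not support that. But both criteria depend on judgment, criterion 16 leaves the earliest 9 to 12 days uncovered, and neither says which limit in criterion 17 applies.
- **The protocol does not contradict its own conversion.** This also stands. Appendix B relates mL to ounces in an instruction about swallowing tablets and never mentions teaspoons. The point rests on the standard size of a teaspoon, which is enough.
- **The safety stakes can be overstated.** Fair. The fatal hemoptysis in Section 9.11 comes from doses of up to 10 mg or 20 mg BID, whereas the starting dose here is 5 mg BID. It shows why the criterion exists, not a risk estimate for patients in the disputed band.
- **Past volumes are recalled, not measured.** True, and 2.5 mL against 5 mL may be hard to separate at interview. That is no reason to leave a twofold disagreement in the written limit.
- **Few patients are affected and no analysis depends on it.** Probably right on the first part, and right on the second. The protocol gives no frequency of recent hemoptysis in this population.

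**Conclusion.** The point holds for criterion 17 as written. Its two limits are presented as equal and differ by a factor of 1.97 to 2.0 with a US or metric teaspoon, or 2.37 with an imperial one. The conflict is confined to episodes above 2.5 mL and up to about 5 mL (5.92 mL imperial) within 6 weeks before treatment; smaller and larger episodes are classified the same way under either unit.

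The factor of 2 is a ratio of thresholds, not of patients. A reader might infer that everyone in the band is enrolled or turned away purely according to the unit a site uses. The documents do not support that, because criteria 16 and 43 can decide some of these cases independently. The number affected is unknown and probably small.

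The DLT rules, response rate, futility rule, sample size and analysis populations do not depend on it. The conclusion assumes only that teaspoon has its standard meaning, since the protocol gives no other. It is worth correcting because it is a wrong figure in a binding eligibility limit with a safety purpose.

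**What to change.** The sponsor should confirm which volume criterion 17 is meant to set and restate the other unit so that the mL figure and the household measure agree, or keep a single unit. The two figures must be reconciled; which volume is clinically right is for the sponsor to decide and is not proposed here.

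The cost is one phrase in the next amendment and a short notice so that all sites apply the same limit. The effect on accrual should be negligible, and no statistical section needs to change.

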## Medications

31. Received systemic antibiotics within 14 days of the initiation of study treatment.

32. Probiotic usage during screening and throughout the study treatment period.

33. Treatment with systemic immunosuppressive medication, including (but not limited to) glucocorticoids with daily doses exceeding an equivalent of 10 mg of prednisone per day, within 14 days prior to the initiation of study treatment.

34. Treatment with vitamin K antagonists.

Note: Therapeutic use of the following agents is allowed:

- Low-molecular-weight heparin
- Direct-acting oral coagulants in alignment with each agent's posology (see Section 6.7.2.2).

35. Received a live-attenuated vaccine within 28 days of the planned start of study treatment or anticipated need to receive such a vaccine during the treatment period and up to 90 days after the last dose of study treatment has been administered.

- Examples of common live-attenuated vaccines include, but are not limited to, MMR, chickenpox/zoster, yellow fever, rabies, BCG, typhoid, and LAIV.

Note 1: Seasonal influenza vaccines for injection are generally killed virus vaccines and are allowed; however, intranasal influenza vaccines are live-attenuated vaccines and are not allowed.

Note 2: COVID-19 vaccines (eg, mRNA) are allowed as long as they are not live vaccines.

36. Treatment with moderate and potent [REDACTED] inhibitors or inducers or drugs that are known to have proarrhythmic potential (see [Appendix C](#)).

Note: A washout period  $\geq 10$  days before the first dose of INCB099280 is required for prior treatment with moderate or potent [REDACTED] inhibitors or inducers.

37. Unable to discontinue medication that is prohibited by this study (see Section [6.7.3](#)) before the initiation of study treatment.

## Organ Function

38. Laboratory values at screening as defined in [Table 6](#).

**Table 6: Exclusionary Laboratory Values**

Laboratory Parameter		Exclusion Criterion
Hematology		
a	Platelets	$< 100 \times 10^9/L$
b	Hemoglobin	$< 9 \text{ g/dL}$ or $< 5.6 \text{ mmol/L}$ (transfusion is acceptable to meet this criterion)
c	ANC	$< 1.5 \times 10^9/L$
Hepatic		
d	ALT	$> 2.5 \times \text{institutional ULN}$
e	AST	$> 2.5 \times \text{institutional ULN}$
f	Total bilirubin	$> 1.5 \times \text{institutional ULN}$ unless conjugated bilirubin $\leq \text{ULN}$ (conjugated bilirubin only needs to be tested if total bilirubin exceeds ULN). If there is no institutional ULN, then direct bilirubin must be $< 40\%$ of total bilirubin.
g	Albumin	$< 3 \text{ g/dL}$
Renal		
h	Calculated CrCl a	$\text{CrCl} < 50 \text{ mL/min}$

**Table 6: Exclusionary Laboratory Values (Continued)**

Laboratory Parameter		Exclusion Criterion
i	Urine protein	$\geq 2+$ by dipstick urinalysis and $\geq 2$ g urinary protein per 24 hours on a 24-hour urine collection or urine protein-to-creatinine ratio $\geq 2$
Coagulation		
j	INR	$> 1.5 \times$ institutional ULN (if not receiving therapeutic anticoagulation) $> 2 \times$ institutional ULN (if receiving therapeutic anticoagulation)
k	PT	$> 1.5 \times$ institutional ULN (if not receiving therapeutic anticoagulation) $> 2 \times$ institutional ULN (if receiving therapeutic anticoagulation)
l	aPTT	$> 1.5 \times$ institutional ULN
Bone profile		
m	Corrected serum calcium	$> 2.9$ mmol/L ( $> \text{Grade } 1$ ) despite maximal antihypercalcemic therapy

a Cockcroft and Gault (1976):  $\text{CrCl} = \{([140 - \text{age}] \times \text{weight [kg]}) / (72 \times \text{serum creatinine})\} \times 0.85$  (if female).

## Diagnostic Assessments

39. Clinically significant and uncontrolled arrhythmia.
40. An average QTcF interval  $> 480$  milliseconds on a triplicate ECG.
41. Left ventricular systolic dysfunction with an LVEF  $< 50\%$ .

## Other Exclusions

42. Pregnant, expecting to conceive, or breastfeeding from consent until 190 days after the last dose of study treatment.
43. History or current evidence of a medical condition, therapy, or laboratory abnormality that, in the opinion of the investigator, might interfere with full participation in the study, increase the risk associated with study participation or the administration of the study medication, confound the results of the study, or make it inappropriate for the participant to take part in this study.
44. The following participants are excluded in France: vulnerable populations according to article L.1121-6 of the French Public Health Code and adults under legal protection, or who are unable to express their consent per article L.1121-8 of the French Public Health Code, not affiliated to a social security per article L.1121-8-1 of the French Public Health Code.

## 5.3. Lifestyle Considerations

### 5.3.1. Meals and Dietary Restrictions

During each administration period (morning/evening), INCB099280 should be administered on an [REDACTED]. Meals that exceed [REDACTED] calories with

█████% calories from fat should be consumed at least █ hours before or after INCB099280 administration. Site staff should discuss light meals or snacks with the participant and provide examples of food consumption that should be avoided within the  $\pm$  █-hour █████ window. An example of a █████ meal in the United States is to be provided as a guide and would include 8 oz of skim [1% fat] milk, 1 boiled egg, and 1 packet of flavored instant oatmeal made with water.

On days of PK sampling, participants should not consume a █████ or █████, █████ within at least █ hours before or after INCB099280 dose administration.

#### **5.3.1.1. █████**

Participants will refrain from consuming █████ containing these restricted █████ from 72 hours before the first dose of study treatment and throughout the study.

